### 5.13 Prior and Concomitant Medications and Treatments

### 5.13.1 Prior Medications and Procedures

All medications administered, and procedures conducted within 28 days prior to the first day of study treatment administration are to be recorded in the medical record. In addition, all prior treatments for the underlying malignancy should be recorded.

# 5.13.2 Concomitant Therapy Requiring Careful Monitoring

Concomitant use of drugs with a potential QT prolongation should be avoided and replaced with alternative treatments. If this is not possible, participants receiving these drugs should be adequately monitored.

These medications include but are not limited to:

- · Fluoroquinolones such as ciprofloxacin and moxifloxacin
- Azole antifungals such as fluconazole and posaconazole
- Serotonin (S-HT3) antagonists such as granisetron and ondansetron

Other examples of drugs known to prolong the QT interval are listed in Appendix 11.5.

### 5.13.3 Prohibited Concomitant Therapy

Anticancer therapy other than the treatment outlined in the protocol is not permitted during the study. If alternative therapy is required for treatment of the participant's disease, the participant should be discontinued from the study treatment.

### 5.13.4 Allowed Concomitant Medications, Procedures, and Treatments

Medications and treatments other than those specified above are permitted during the study. All intercurrent medical conditions and complications of the underlying malignancy will be treated at the discretion of the Investigator according to acceptable local standards of medical care.

If clinically indicated, palliative biliary decompression procedures will be permitted on-study after discussion with the PI.

Participants should receive analgesics, antiemetics, anti-infectives, antipyretics, blood products, and any other best supportive care measures (excluding anticancer therapy) as necessary, assuming no drug interaction potential.

Growth factors (granulocyte colony-stimulating factor [G-CSF], granulocyte-macrophage colonystimulating factor [GM-CSF]) can be used to support participants who have developed dose-limiting Grade 4 neutropenia or Grade 3 neutropenia with fever and/or infection. The use of erythropoiesis stimulating agents is permitted according to the American Society of Clinical Oncology Guidelines (Rizzo, Brouwers et al. 2010).

All concomitant medications and any procedures performed during the study, including those used to treat AEs, are to be recorded.

# 6.0 Study Processes and Assessments

### 6.1 Schedule of Events

Table 3 provides the schedule of assessments for this study. Pre-screening or screening for IDH1 will occur via CLIA certified standard of care sequencing. After obtaining written informed consent for the study overall, all participants will undergo Screening procedures to determine eligibility within 28 days prior to the start of study treatment on C1D1. Participants are to attend study center visits as outlined in the Schedule of Assessments (Table 3).

An EOT Visit will be conducted as soon as possible after discontinuing study treatment (within 5 days of last dose of study treatment, if study drug dosing has not been delayed); in addition, participants are to attend a Follow-up Visit 28 days (no more than 33 days) after the last dose of study treatment for final safety assessments. If a participant's dose is held and it is subsequently decided to discontinue treatment, the EOT Visit should be conducted as soon as possible, within 28 days (and no more than 33 days) after the last dose of study treatment for final safety assessments.

# Table 3: Study Calendar Showing Schedule of Assessments

2								.		Post	
isit/Cycle:	Screening	-	cle 1 days)		cle 2 days)	-	cle 3 days)	Cycle 4+  (±2 days)	EOT	Treatment Follow-up	PFS Follow- up
Study Day:	D-28	D1	D15	D1	D15	D1	D15	D1		D+28	
Informed Consent	x										
Review Entry Criteria	X										
Demographics	X										
Disease History	X										
Medical and Surgical History	X										
Medication History	x	x	x	x	x	x	x	x		x	
Complete Physical Exam	x	x				X		x		X	x
Symptom Directed Physical Exam			x	х	x						
Vital Signs	x	x	x	X	x	x		x		x	x
ECG	X	X	X	X	I X	х		X		x	

Visit/Cycle:	Screening	Cyc (±2 c	Cycle 1 (±2 days)	Cyc (±2 c	Cycle 2 (±2 days)	Cyc (±2 c	Cycle 3 (±2 days)	Cycle 4+  (±2 days)	EOT	Post Treatment Follow-up	PFS Follow- up
Study Day:	D -28	D1	D15	D1	D15	D1	D15	D1	Δ	D +28	
ECOG PS	×	×		×		×		×		X	×
Fresh/Banked Tumor Tissue 	×			×							
					Labora	tory Eve	Laboratory Evaluations 	2			
Hematology	×	×	×	×	×	×	×	×		×	
Serum Chemistry	×	×	Х	Х	×	×	Х	×		×	
Thyroid Studies	×			×		Х		X 		X	
Pregnancy Test 	×			×		×		х			
Correlative Blood – PBMC, serum 		×	×	×		×		×		×	
Germline DNA		×									

Visit/Cycle:	Screening		/cle 1 days)		ycle 2 2 days)		ycle 3 2 days)	Cycle 4+ (±2 days		Posi Treatment Follow-up	PFS Follow- up
Study Day:	D-28	D1	D15	D1	D15	D1	D15	D1	[	D+28	
Correlative Blood - ctDNA		х	х			х		Х		Х	
2-HG PD Analysis (plasma)⁴		х		х				Х		Х	
Stool	X										

reening	-	vcle 1 days)	Cyc (±2 d		Cyc (±2 d		Cycle 4 +  (±2 days)	EOT	Post Treatment Follow-up	PFS Follow- up
0-28	D1	D15	D1	D15	D1	D15	D1		D+28	
				Regis	tration and	d Treatme	ent:			
Х										
	x		x		x		x			
			x		x		x		x	
Tumor Assessments										
x					8 weeks(	±7 days)	after Cycle 1	including EOT	and PFS follow-up	
		 		Other	Clinical A	ssessmer	nts			
	X	x	x	x	X		x		x	XS
	x	x	x	x	x		x		x	x

Abbreviations: D = Day; DNA= deoxyribonucleic acid; ECOG = Eastern Cooperative Oncology Group; EQT= end of treatment; PFS = progression-free survival; PS= performance status; RECIST = Response Evaluation Criteria in Solid Tumors

Archival tissue to be submitted on all patients. At least 10 (solid tumor) patients to be biopsied, pending funding

- Female participants with reproductive potential must have negative serum pregnancy testing within 24 h prior to the initial administration of study drug, then every 4 ± 1 week, or a negative confirmation from an obstetrician in case of equivocal serum pregnancy results. Females of reproductive potential are defined as sexually mature women who have not undergone a hysterectomy, bilateral oophorectomy, or tubal occlusion or who have not been naturally postmenopausal (ie, who have not menstruated) for at least 24 consecutive months (ie, have not had menses at any time in the preceding 24 consecutive months).
-  ctDNA to be collected C1D1, C1D15, C3D1, C4D1 (time of pt response assessment) and at time of progression. PBMCs to be collected C1D1, C1D15, C2D1, C3D1, C4D1 (time of pt response assessment) and at time of progression.

Germline DNA to be collected C1D1

Serum to be drawn C1D1, C1D15, C2D1, C3D1, C4D1 (time of pt response assessment) and at the time of progression.

Modification for 2-HG levels: Drawn on C1D1 (as baseline), at 1 month (C2D1), 3 months (C4D1) and at time of disease progression

Submit all required materials (eligibility checklist, source documentation, and signed consent form) to confirm eligibility and required pre-study procedures to the CRA a minimum of 48 h prior to the participant's scheduled therapy start date. Full details listed in Registration Procedures

Note that nivolumab will be dosed Q28 days via IV infusion, while ivosidenib will be continuous PO daily dosing

After cycle 3 (i.e., from C4 onwards), study visits will be monthly.

-  SAEs occurring within 100 days post last study drug dose must be reported to BMS World Wide Safety and Agios
-  Specific imaging modalities detailed under section 6.5 (Efficacy Assessments)
-  As clinically indicated
-  See Section 1.3.4 for research blood draw time points
-  See Section 6.4.3 Safety Laboratory Assessments

### 6.2 Informed Consent

A complete description of the study is to be presented to each potential participant and a signed and dated informed consent is to be obtained before any study specific procedures are performed. A legally authorized representative may consent on behalf of a participant who is otherwise unable to provide informed consent if acceptable to and approved by the site's Institutional Review Board (IRB)/Independent Ethics Committee (IEC).

Demographic Data and Medical, Surgical, and Medication History

Subject demographic data, including gender, date of birth, age, race, and ethnicity, will be obtained during Screening, according to applicable local regulations.

A complete medical and surgical history, including the site of underlying sites of malignancy and the date of confirmation of the histologic diagnosis of the underlying malignancy will be obtained during Screening. The medical history is to include all relevant prior medical history as well as all current

medical conditions.

All medications administered and procedures conducted within 28 days prior to C101 should be reported in the medical record. In addition, all prior treatment regimens for the underlying malignancy will be reported.

### 6.3 Gene Mutation Analysis and Molecular Characterization

Tissue from a pre-treatment fresh or banked tumor biopsy will be required for all screened participants. Corresponding pathology report is also required if available.

### 6.4 Safety Assessments

### 6.4.1 Physical Examination and ECOG Performance Status

A complete physical examination, including assessment of weight, will be obtained at Screening, C1D1, C301 and every Day 1 of each cycle thereafter, EOT and post treatment follow up visit and PFS follow up. A symptom directed physical examination should be completed on C1D15, C2D1, and C2D15. Height will be obtained at the Screening Visit only. Participants should be monitored for rash at physical examinations and during assessments of adverse reactions.

Determination of ECOG PS will be performed at Screening, on Day 1 of each treatment cycle thereafter, at the EOT Visit, at the Post Treatment Follow-up Visit, and PFS follow up. See Appendix 11.1 for ECOG PS scoring.

### 6.4.2 Vital Signs and ECG

Vital signs, including systolic and diastolic blood pressure, heart rate, respiratory rate, and temperature, will be obtained at Screening, Days 1 and 15 of Cycles 1 and 2, on Day 1 of each treatment cycle thereafter, EOT and post treatment follow up Visit and PFS follow up. Assessments should be conducted while the participant is seated or supine.

ECG will be obtained at Screening, Days 1 and 15 of Cycles 1 and 2, on Day 1 of each treatment cycle thereafter, EOT and post treatment follow up Visit. Refer to section 5.7 for management of QT prolongation.

### 6.4.3 Safety Laboratory Assessments

Clinical laboratory evaluations are to be performed by the local laboratory.

Clinical laboratory evaluations are to be conducted according to the Schedule of Assessments (Table 3). Clinical laboratory evaluations may be collected up to 24 h prior to study visit as long as the labs were collected within the visit window (±2 days). In addition, all clinically significant laboratory abnormalities noted on testing will be followed by repeat testing and further investigated according to the judgment of the Treating Investigator.

The safety laboratory parameters to be evaluated by the Treating Investigator are:

**Hematology:** Hemoglobin, red blood cell (RBC) count, white blood cell (WBC) count and differential {% neutrophils, % bands), platelet count with differential

**Chemistry:** Sodium, potassium, calcium, magnesium, phosphorus, albumin, glucose, blood urea nitrogen (BUN), creatinine, uric acid, lactate dehydrogenase (LOH), alkaline phosphatase (ALP), AST, ALT, total bilirubin, direct bilirubin

**Thyroid Studies:** Thyroid stimulating hormone (TSH), total triiodothyronine (T3, *If TSH is abnormal*), free thyroxine (T4, *If TSH is abnormal*)

Blood for hematology and chemistries is to be obtained at screening, CI - C3 days 1 and 15, on Day 1 of every treatment cycle thereafter, and at the EOT Visit. If assessments for hematology and serum chemistry were performed within 3 days prior to CIDI, these do not need to be repeated at the CIDI Visit.

**Pregnancy Test:** All WOCBP must have a negative pregnancy test to be eligible. Pregnancy testing to be done every 4 weeks±l week while on study treatment.

### **Adverse Events**

All AEs will be graded using the NCI CTCAE version 5 grading system (Appendix 11.7).

### 6.5 Efficacy Assessments

### 6.5.1 Response to Treatment

The efficacy of ivosidenib and nivolumab will be evaluated by assessing response to treatment according to RECIST vI.1 (Appendix 11.8) or RANO Criteria (Appendix 11.9) (Eisenhauer, Therasse et al. 2009).

Radiographic assessments (CT or MRI) to obtain tumor measurements are to be conducted every 8 weeks (±7 days) from CIDI, independent of dose-delays and/or dose interruptions, and/or at any time when progression of disease is suspected. CT imaging of the chest, abdomen, and pelvis (torso) with triphasic IV contrast (30 millisieverts [mSv] per scan) should be performed at baseline and on study for solid tumor patients (not glioma patients). For participants with allergy to IV iodine contrast, CT of the chest without IV contrast and MRI of the abdomen with IV contrast should be performed at baseline and on study. For patients with solid tumors, brain scans with CT (2 mSv per scan) or MRI should be performed at baseline in participants with known treated brain metastases and on study at the same imaging time points as Torso imaging.

For the glioma cohort, MRI with contrast is required for baseline and response assessments, and CT is only allowed if an MRI is contraindicated (in the view of the treating physician). Bone scans (4 mSv per scan) will be performed at baseline if disease is suspected and on study as appropriate as the same imaging time points as Torso imaging. Any ancillary findings on the radiographic assessments will be communicated to the appropriate physician for notification to the participant. The same method (CT or MRI) should be used consistently for any given participant. For participants who discontinue study drug for reasons other than disease progression, an assessment will be conducted at the EOT Visit and every 8 weeks thereafter (with the exception of those participants who initiate a new cancer therapy after discontinuing study treatment) until any of the conditions for withdrawal of study treatments are met - as detailed in 4.4.1.

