Participants may continue with their assigned study treatment until disease progression, development of unacceptable toxicity, confirmed pregnancy, death, withdrawal of consent, the participant is lost to follow-up, or the Lead Principal Investigator (PI) ends the study, whichever occurs first. For participants who are determined to be on ivosidenib upon radiographic disease progression and demonstrate clinical benefit, treating investigators, with consult from the Lead PI, may keep the participants on ivosidenib after the disease progression.

**Post-Treatment Follow-up Visit:** A Post-Treatment Follow-Up Visit for safety will occur 28 days (no more than 33 days) after the last dose of study drug. Every effort must be made to perform protocol-specified evaluations unless consent to participate in the study is withdrawn. Assessments to be performed at the Follow-up Visit are included under study assessments. If a participant's dose is interrupted for 28 days and then the participant discontinues study participation, the EOT Visit will serve as the Post-Treatment Follow-up Visit.

**PFS Follow-up:** Participants who discontinue study treatment for reasons other than disease progression or withdrawal of consent will be followed in PFS follow-up (every 8 weeks through week 48, and every 8 weeks thereafter) until documented disease progression, death, or the initiation of new cancer therapy. If a participant begins a new anticancer therapy during PFS follow-up, information on the new anticancer therapy will be collected.

**End of Study:** End of study is defined as the point in time when all participants have died, withdrawn consent, or been lost to follow-up.

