# 4.4.1 Withdrawal from Study Treatment

Participants may discontinue or be discontinued from study treatment at any time. In this situation, a participant without documented progressive disease by the treating investigator should be followed for tumor assessments until the development of progressive disease and/or survival. Participants will be discontinued from study treatment for the following reasons:

- Grade 4 QTcF prolongation.
- Disease progression (participants who are, in the opinion of the treating investigator, benefiting from treatment [e.g., slow progression or immune-related response evaluation] may be allowed to continue on study treatment)
- Severe or unacceptable toxicity
- Death
- Lead Investigator decision
- Subject decision to withdraw from treatment
- Protocol violation: non-adherence to study treatments as required for evaluability (detailed in section 8.1.1) or other protocol requirements.
- Confirmed pregnancy (study therapy should be immediately interrupted based upon a positive urinary human chorionic gonadotropin [hCG] test, and permanently discontinued if confirmed by a serum -hCG test)
- Lost to follow-up

All AEs should be followed until resolution or for a period of 28 days from the last dose of study treatment, whichever is shorter. If the participant withdrew from treatment because of an AE, every

effort must be made to perform protocol-specified safety follow-up procedures. All SAEs that occur up to 100 days post last dose of nivolumab must be reported to BMS World Wide Safety.

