### 4.4.2 Study Participation Termination

Participants who discontinue treatment without disease progression or death will continue to be followed for PFS every 8 weeks after the EOT Visit (±5 days) until disease progression, death, start of subsequent anticancer therapy, or withdrawal of consent until 6 months after the last enrolled patient begins treatment. Participants will be terminated from the study for the following reasons:

- Death
- Withdrawal of consent for follow-up
- Loss to follow-up
- Termination of the study

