# 5.5 Criteria for Dose Modification, Discontinuation of Study Treatment, and Continuation Beyond Radiographic Progression

### 5.5.1 Study Treatment Dose Modification and Discontinuation Criteria

### 5.5.1.1 Dose Modifications and Delays

Dose reductions or dose escalations of nivolumab are not permitted. Nivolumab may continue if the ivosidenib is held unless the hold of ivosidenib is for more than 28 days. If a safety issue arises that is related to nivolumab, the nivolumab should be withheld or permanently discontinued (Section 5.9). In such a case, continuing ivosidenib may be allowed after consultation with the PI.

For any AE, including AEs not specifically mentioned in Table 1, the treating investigator may decide to delay dosing or modify the dose of ivosidenib based on clinical judgment. Dose modifications of ivosidenib from 500 mg to 250 mg will be permitted on study for management of AEs (Table 1). If more than one AE occurs that would require a dose modification, upon resolution of all AEs to baseline or Grade 1, ivosidenib should be dose reduced to 250 mg. Dose reductions below 250 mg are not permitted. If the AE is thought to be related to the ivosidenib, the nivolumab will continue to be dosed as per protocol schedule.

Dose delays for reasons other than management of AEs are discouraged. Dose delays up to 28 days will be permitted at the discretion of the lead investigator.

If the participant cannot resume ivosidenib within 28 days, the participant should be discontinued from both study medications. If ivosidenib is discontinued, the participant will complete the EOT and Followup Visits, and then enter PFS follow-up (if disease has not progressed). Exemptions may be considered for those participants who are determined by the investigator to have received clinical benefit from treatment. If a dose is delayed for the management of an AE, the participant should resume the study at the next planned visit within a dosing cycle. This determination will be at the discretion of the treating physician.

AEs	Action
Grade 2 nausea or vomiting (related or unrelated)	
 
Consider holding dose of ivosidenib until resolution of AE to Grade 
 
within 28 days of supportive therapy.
 
 
 
Manage with supportive therapy according to the institutional standard of care.
 
May resume ivosidenib at same dose.
 

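### Section 6.5.1 ends post-treatment scans on the Section 4.4.1 reasons for stopping treatment, which conflicts with the PFS follow-up rules elsewhere and puts PFS6 ascertainment at risk

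*Combined protocol and SAP*

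**What the plan says.** The last sentence of Section 6.5.1 covers participants who stop study drug for reasons other than progression. For them "an assessment will be conducted at the EOT Visit and every 8 weeks thereafter", with an exception for those who start a new cancer therapy, and this continues "until any of the conditions for withdrawal of study treatments are met", with a pointer to Section 4.4.1.

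The Section 4.4.1 list opens: "Participants will be discontinued from study treatment for the following reasons". The reasons are Grade 4 QTcF prolongation, progression, severe or unacceptable toxicity, death, Lead Investigator decision, the participant's decision to leave treatment, protocol violation, confirmed pregnancy and loss to follow-up.

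Other parts of the protocol set a different end to follow-up:

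- The opening paragraph of 4.4.1, ahead of that list, says that a participant who leaves treatment without documented progression "should be followed for tumor assessments until the development of progressive disease and/or survival".
- The PFS follow-up paragraph of 3.1 runs follow-up every 8 weeks "until documented disease progression, death, or the initiation of new cancer therapy".
- Section 4.4.2 says: "Participants who discontinue treatment without disease progression or death will continue to be followed for PFS every 8 weeks". It ends this at progression, death, subsequent anticancer therapy or withdrawal of consent, within a calendar limit.
- Section 5.5.1.1 has a participant who discontinues ivosidenib complete the EOT and Follow-up Visits and "then enter PFS follow-up (if disease has not progressed").
- Section 5.10.1 sends participants whose treatment was withheld for toxicity and not restarted into PFS follow-up.
- The tumor assessment row of Table 3 covers EOT and PFS follow-up.

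**The concern.** The stop in 6.5.1 is tied to the wrong event. It applies to people who are already off drug, yet its end condition is a list of reasons for coming off drug. A participant who stopped for toxicity has met a listed condition by the EOT visit. On the literal wording, the 8-weekly scans ordered earlier in the sentence are never due.

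This matters because PFS6 is one of the two components of the decision outcome. Section 8.2.1 counts a participant as positive only with at least a partial response and PFS6 scored Yes. It allows only Yes or No and gives no rule for a month-6 status that was not observed. Under 8.1.2, receiving 75% of the first cycle of ivosidenib and one nivolumab dose meets the treatment requirement for evaluability. A responder who stops early can therefore stay in the denominator while month-6 status is unknown.

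For PFS, Section 8.2.3 censors progression-free survivors at their last negative examination. If imaging ended at EOT, censoring would fall at EOT, for reasons such as toxicity that may be related to outcome.

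Stops without progression are foreseeable here. Section 5.5.1.1 takes participants off both drugs if ivosidenib cannot resume within 28 days, with limited exemptions, and Section 5.8 lists many events that end nivolumab permanently.

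**Working it through.** **Step 1. Compare the end conditions.** All rows concern a participant who is off treatment without progression.

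| Place | What continues | When it ends |
|---|---|---|
| 6.5.1, last sentence | Scan at EOT, then 8-weekly | Any 4.4.1 reason for leaving treatment; new cancer therapy excepted |
| 4.4.1, opening | Tumor assessments | Progression and/or survival |
| 3.1, PFS follow-up | 8-weekly follow-up | Progression, death or new cancer therapy |
| 4.4.2 | 8-weekly PFS follow-up after EOT | Progression, death, new anticancer therapy or withdrawal of consent, within a calendar limit |
| 5.5.1.1 | PFS follow-up | Not stated |
| 5.10.1 | PFS follow-up | Not stated |
| Table 3, tumor row | 8-weekly scans, including EOT and PFS follow-up | Not stated |

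Only 6.5.1 uses reasons for leaving treatment as the end of imaging. The other six places continue follow-up.

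**Step 2. Test the 6.5.1 clause on a case.** A participant stops for severe toxicity at month 4 without progression. The 6.5.1 sentence applies, because the reason is not progression, and the EOT scan is done. Severe toxicity is on the 4.4.1 list, so a listed condition already holds and the next 8-weekly scan is not due. Under 3.1 or 4.4.2 the same participant is followed past month 6. The two instructions give different data for PFS6.

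**Step 3. Reproduce the design.** From 8.2.1: 18 participants in stage 1, continue with 3 or more positives, add 17, and reject with 7 or more positives of 35. The rejection probability at true rate p is

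R(p) = sum over x = 3 to 18 of P(X1 = x) × P(X2 ≥ 7 − x), with X1 ~ Bin(18, p) and X2 ~ Bin(17, p).

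- R(0.10) = 0.0474, within the stated 0.05.
- R(0.30) = 0.9016, matching the stated 90%.

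The design figures stand, and correcting the clause changes none of them.

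**Step 4. Illustrate the scale.** The documents give no rate of stopping before month 6 without progression for this combination. The nearest figure is for ivosidenib alone, in the AG120-C-002 cholangiocarcinoma cohort (Section 1.4.3.1). Of 48 treated, 25 discontinued: 19 for progression, and 2 each for adverse events, withdrawal of consent and other reasons. Withdrawals of consent are left out, because the corrected rule would also end follow-up for them.

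- Adverse events only: 2/48 = 4.2%.
- Adverse events plus other reasons: 4/48 = 8.3%.

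Assume that a share f of true positives goes unscanned at month 6 and is scored No. The effective rate is then 0.3 × (1 − f):

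| f | Effective rate | Power |
|---|---|---|
| 0 | 0.3000 | 0.902 |
| 2/48 | 0.2875 | 0.875 |
| 4/48 | 0.2750 | 0.842 |

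These figures are illustrations. The 48-patient cohort counts stops at any time up to its data cutoff, with 23 still on treatment, and it counts all patients rather than responders. The calculation also assumes that every affected participant goes unscanned.

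**The case against.** A reader might infer from 6.5.1 that participants who stop without progression get no scans after EOT and that their PFS6 and PFS are lost. The documents do not support that. Six other places require continued follow-up or tumor assessment, and one of them is the opening of 4.4.1, the section that 6.5.1 cites. Sections 5.5.1.1 and 5.10.1 deal directly with treatment held and not resumed, including for toxicity, and send the participant to PFS follow-up. Section 6.1 sends sites to Table 3 for visits, and its tumor row includes PFS follow-up. Even on the literal clause the EOT scan is done, PFS is censored rather than missing, and PFS6 is affected only for stops before month 6.

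It can also be said that the self-cancelling reading is strained. Ordering 8-weekly scans and exempting those on new therapy would be pointless if the stop were already met. A sensible reader would apply only the conditions that can newly arise off drug, such as progression, death or loss to follow-up.

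Most of this stands, and it limits the consequence to a risk. It does not remove the conflict. The clause says any of the listed conditions, and the list includes toxicity and investigator decision. Section 6.5.1 is the efficacy-assessment section, and Table 3 sends readers to Section 6.5 for imaging modalities while giving no end condition of its own. The radiographic paragraph of 3.1 mentions only an EOT assessment for these participants. Two centers could reasonably follow different sentences.

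How to score an unobserved PFS6 is a separate gap. The clause does not create it, but could add to the number of participants it affects.

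**Conclusion.** The point holds as a conflict between sections. The end condition in 6.5.1 is circular for the participants it addresses and disagrees with 3.1, the opening of 4.4.1, 4.4.2, 5.5.1.1, 5.10.1 and Table 3. The consequence is conditional: a site that follows 6.5.1 literally could stop imaging a non-progressed participant before month 6, leaving PFS6 unobserved and PFS censored at EOT for reasons that may relate to outcome. The stronger inference, that all such participants go unscanned and their endpoints are lost, fails because most of the document says otherwise.

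The actual effect cannot be sized from the documents. The fall in power from 90% to about 87% to 84% is illustrative. It rests on three assumptions: that 4% to 8% of true positives are affected, that sites follow the literal clause for all of them, and that they are scored No. The correction is worth making because it costs little and protects a component of the decision outcome.

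**What to change.** In 6.5.1, replace the end clause and its pointer to 4.4.1 with the PFS follow-up stop from 3.1 and 4.4.2 combined: documented progression, death, start of new anticancer therapy, or withdrawal of consent for follow-up. The consent item comes from 4.4.2, since the PFS follow-up stop in 3.1 does not list it. Add that stopping study treatment without progression does not end tumor assessments.

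The same edit should settle a separate mismatch in the follow-up period. Section 4.4.2 limits PFS follow-up to 6 months after the last enrolled patient starts treatment, while 2.2.2 and 8.2.3 run PFS to 18 months after the last participant starts.

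The 6.5.1 change costs a sentence or two in the next amendment. It adds no scans beyond those the other sections already require, and changes no treatment rule and no design figure.
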